2. All subjects will undergo an EOT assessment within 7 days after the last dose of IMP (for combination, this is to occur after all 3 IMPs have been discontinued). However, when this is not possible (e.g., dose delay more than 7 days), EOT assessment can be performed at the 30-day safety follow-up visit. A second Safety Follow-up will occur 100 (+5) days after last nivolumab dose or ipilimumab if no other anti-cancer therapy is initiated.
3. Subjects who discontinue study treatment for reasons other than disease progression or withdrawal of consent and are alive by EOT will enter PFS follow-up with the same schedule of assessments as before study treatment discontinuation, until documented disease progression, death, start of subsequent anti-cancer therapy, withdrawal of consent, or the end of study/study termination.
4. Allocation of IMP will occur via RTSM.
5. Height is to be obtained only at Screening assessment.
6. Systolic and diastolic blood pressure, heart rate, respiratory rate, and temperature. Assessments should be conducted while the subject is seated or supine.
7. Subjects with a QTcF of \geq 450 msec at baseline will not be allowed to enroll in the study. Up to three 12 lead ECG tests under stable condition can be performed at each visit during screening and throughout treatment and study follow-up.
8. ECG can be performed at any time during the study visit (on-site or at local clinic); however, it is required once weekly for the first 3 weeks of treatment, and then once every cycle for the duration of therapy.
9. Hematocrit, hemoglobin, red blood cell count, white blood cell count with differential, and platelet count. Hemoglobin criteria of \geq 9.0 g/dL or \geq 5.6 mmol/L at Screening must be met without packed red blood cell transfusion within the prior 2 weeks. Subjects can be on stable dose of erythropoietin (\geq approximately 3 months). On C1D1, assessments should be conducted prior to IMP administration.
10. Sodium, potassium, chloride, calcium, magnesium, phosphorus, carbon dioxide, albumin, glucose, blood urea nitrogen (BUN)/UREA, creatinine, alkaline phosphatase, alanine aminotransferase, aspartate aminotransferase, gamma glutamyl transferase, total bilirubin, direct bilirubin, and indirect bilirubin. On C1D1, assessments should be conducted prior to IMP administration.
11. Activated partial thromboplastin time and either prothrombin time or international normalized ratio.

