23. Blood samples for exploratory biomarker assessments, including plasma circulating tumor DNA, will be collected at Screening and Day 1 of every cycle through Cycle 6, followed by every 6 months thereafter, and at EOT.
24. From the time of informed consent signing through the first dose of IMP, SAEs resulting from a study-related procedure and assessed as related to that procedure, as well as all fatal AEs whether or not related to research procedures, must be recorded. All AEs will be recorded from all subjects from the date of first dose through 30 days following the last dose of ivosidenib and/or nivolumab or ipilimumab, whichever occurs later. Following the 30-day Safety Follow-up period, any SAEs that occur within 100 days after last dose of immunotherapy are to be reported, or until the subject initiates another anti-cancer therapy, whichever is earlier. Only SAEs that are considered as related to either IMP by the Investigator are to be reported after the respective Safety Follow-up periods. Fatal events, related or not to the research, occurring after ICF signature and before first IMP administration, must be reported on an AE form.
25. All concomitant medications/procedures within 21 days of the first dose of IMP through 30 days (+ 5 days) after the last dose of ivosidenib and/or immunotherapy and through 100 days after the last dose of immunotherapy (whichever is later) are to be reported on the eCRF.
26. Subjects will be contacted every 12 weeks (\pm 2 weeks) after the subject experiences documented disease progression or begins subsequent anti-cancer therapy for up to 2 years after the last subject has been enrolled, or until death, lost to follow-up, withdrawal of consent from overall study participation, or Sponsor ending study, whichever occurs first.

Table (4.1.2) 2 - Pharmacokinetic and Pharmacodynamic Sampling for Subjects in the Safety Lead-in Phase: Ivosidenib in Combination with Nivolumab and Ipilimumab

Visit/Cycle:	Screening	Cycle 1 (21 Days)		Cycle 2 (21 Days)	Cycle 3 (21 Days)	Cycle 4 (21 Days Each Cycle)	Cycle 5 and Beyond (28 Days Each Cycle)
Study Day:	D-28 to D-1	D1	D15 (± 2 Days)	D1 (± 2 Days)	D1 (± 2 Days)	D1 (± 2 Days)	D1 (± 2 Days)
Blood Sample for Ivosidenib PK Pre-dose ^{1,2,3}		X	X	X	X	X	X ³
Blood Sample for PD (2-HG) Pre-dose ^{1,2,3}		X	X	X	X	X	X ³
Blood Sample for Nivolumab PK and Nivolumab ADA Pre-dose ^{1,2,4}		X		X	X	X	X ⁴
Blood Sample for Ipilimumab PK and Ipilimumab ADA Pre-dose ^{1,2,5}		X		X	X	X	

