8.10.1. Time Frame for AE Reporting

Any event meeting the above-mentioned definitions (see Section 8.3; [Figure \(8.10.1\) 1](#)) must be reported to the Sponsor on an AE form if it occurs:

- Before the first administration of IMP, for fatal events and events related to the research.
- At any time after the first administration of IMP.
- Up to 30 calendar days after the subject's last administration for all AEs and AESIs (including overdose).
- Up to 90 calendar days after the subject's last administration for all SAEs, or until the subject initiates new anti-cancer therapy, whichever is earlier.
- Up to 180 calendar days after the subject's last administration for all pregnancies and exposures during breastfeeding, or until the subject initiates new anti-cancer therapy, whichever is earlier.
- Irrespective of the time of onset in case of SAEs assessed as related to the research.

Of note, non-fatal events occurring between the signature of the ICF and the first administration of the IMP for which the Investigator does not consider an association with the research must be reported as medical history or as signs or symptoms related to the studied disease in the dedicated form of the eCRF.

Fatal events, related or not to the research, occurring after ICF signature and before first IMP administration, must be reported on the AE form.

Figure (8.10.1) 1 - Rules for Adverse Event Reporting

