10.1.6.2. Analysis of Secondary Safety Endpoints

Safety summaries will contain only data collected during the on-treatment period, unless otherwise specified. Safety data will be summarized. In general, the on-treatment period is defined as the time from the date of the first dose of study drugs to 30 days from the last dose of study drugs. For immune-mediated adverse events, the on-treatment period is defined as the time from the date of the first dose of study drugs to 100 days from the last dose of nivolumab.

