4.2. General definitions

- Baseline is defined as the last available observation prior to the first dose of any investigational medicinal product (IMP) on C1D1. Assessments performed on the same day of first dose will be assumed to happen before first dose, unless the protocol schedule states otherwise or information about the time is available.
- In general, the on-treatment period is defined as the time from the date of the first dose of any IMP to 30 days from the last dose of IMPs. For immune-mediated adverse events (IMAEs), the on-treatment period is defined as the time from the date of the first dose of any IMP to 100 days from the last dose of nivolumab.

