5.4.1.2. Adverse Events

Definition:

- Treatment-Emergent Adverse Events (TEAEs) are defined as all adverse events:
 - which occur or worsen between the first IMP administration date of any drug (included) and the last IMP administration date of any drug + 30 days (included), or between the first IMP administration date of any drug (included) and the last nivolumab administration + 100 days (included) for IMAEs,
 - The seriousness and the relationship with the IMPs of the adverse event are based on investigator opinion.

Analysis:

Adverse events will be coded according to MedDRA dictionary, and their severity classified according to National Cancer Institute Common Terminology Criteria for Adverse Events (NCI CTCAE) v5.0.

Number of events, number and percentage of patients reporting at least one event will be presented in a summary table for TEAEs by SOC, PT and severity.

An overall summary with number and percentage of patients in the following categories will be presented:

- All TEAEs.
- Treatment-related (for any drug) TEAEs.
- Ivosidenib-related TEAEs.
- Nivolumab-related TEAEs.
- Ipilimumab-related TEAEs.
- Grade 3 or higher TEAEs.
- Grade 3 or higher treatment-related TEAEs.
- SAEs.
- Treatment-related SAEs.
- AESIs.
- TEAEs leading to treatment discontinuation of any study drug.
- TEAEs leading to dose reduction of ivosidenib.
- TEAEs leading to on-treatment deaths.

Listings will be provided for TEAEs, SAEs, TEAEs leading to treatment discontinuation of any study drug, and TEAEs leading to on-treatment death.

The date/time of onset, date/time of recovery, action taken with IMPs, seriousness criteria and outcome will also be included in listings.

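### Immune-mediated AEs count as treatment-emergent to 100 days after last nivolumab, but non-serious AEs need be recorded only to 30 days after the last study drug, so late ones may be under-counted

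*SAP*

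**What the plan says.** **Analysis window.** SAP 5.4.1.2 takes TEAEs to be all adverse events that start or worsen in a defined period. For IMAEs that period is "between the first IMP administration date of any drug (included) and the last nivolumab administration + 100 days (included) for IMAEs". SAP 4.2 gives the on-treatment period for IMAEs as running from "the first dose of any IMP to 100 days from the last dose of nivolumab", and protocol 10.1.6.2 has "the time from the date of the first dose of study drugs to 100 days from the last dose of nivolumab". None of the three limits the window to serious events, and none ends it when new anti-cancer therapy starts.

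**Recording window.** Footnote 24 to the schedule of assessments (protocol 4.1.2, repeated for the UK in Appendix 13) says: "All AEs will be recorded from all subjects from the date of first dose through 30 days following the last dose of ivosidenib", with the limit running from whichever of the three drugs stops last. After that, "any SAEs that occur within 100 days after last dose of immunotherapy are to be reported, or until the subject initiates another anti-cancer therapy". Protocol 8.10.1 sets 30 calendar days from the "last administration for all AEs and AESIs (including overdose") and 90 calendar days from the "last administration for all SAEs, or until the subject initiates new anti-cancer therapy, whichever is earlier". Both places keep SAEs judged related reportable without a time limit.

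**Late visit.** Footnote 2 to the same schedule says: "A second Safety Follow-up will occur 100 (+5) days after last nivolumab dose or ipilimumab if no other anti-cancer therapy is initiated".

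**The concern.** Followed as written, the two sets of rules do not meet. A non-serious IMAE that starts after required recording has ended, but within 100 days of last nivolumab, is a TEAE by definition, yet no rule obliges a site to enter it. Protocol 8.7 expects immune-related events as late as several months after the last dose, so the uncovered stretch is one where events are foreseen.

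AEs, AESIs and SAEs are primary endpoints of the Safety Lead-in, the only phase that ran. SAP section 5 drops most tables but keeps the TEAE summaries. The rows exposed are all TEAEs, treatment-related TEAEs and the drug-specific related rows, and also the Grade 3 or higher rows where such an event is not serious. A reader who sees a 100-day definition would take it that events were collected for 100 days.

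**Working it through.** No figure in the plan has to be reproduced; the check is date arithmetic.

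**Inputs**
- IMAE window ends 100 days after last nivolumab (SAP 4.2 and 5.4.1.2; protocol 10.1.6.2).
- Required recording of non-serious AEs ends 30 days after the last dose of any study drug (footnote 24; 8.10.1).
- The synopsis has all AEs reported during a 30 (+5)-day follow-up period, which could be read as running to day 35.
- k = days from last nivolumab to the last dose of any study drug. Protocol 8.12.2 lets ivosidenib continue after immunotherapy stops, so k can exceed 0. Ipilimumab is not continued alone, so last immunotherapy is taken as last nivolumab.

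**Uncovered days for non-serious IMAEs**

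Recording ends at k + 30 days after last nivolumab, so the gap is max(0, 100 − (k + 30)) = max(0, 70 − k). Reading the follow-up period to day 35 gives max(0, 65 − k).

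| k (days) | Gap, 30-day reading | Gap, 35-day reading |
|---|---|---|
| 0 | 70 | 65 |
| 14 | 56 | 51 |
| 28 | 42 | 37 |
| 42 | 28 | 23 |
| 56 | 14 | 9 |
| 70 or more | 0 | 0 |

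**New anti-cancer therapy (assumed example).** The 100-day visit and the requirement for SAEs not judged related both stop when new therapy starts; the IMAE window does not. If new therapy starts on day t, the window outlasts them by max(0, 100 − max(t, 30 + k)) days. With t = 45 and k = 0 this is 100 − 45 = 55 days.

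**SAE limits (secondary).** Reading last administration in 8.10.1 as the last dose of any study drug, its limit falls k + 90 days after last nivolumab. Footnote 24 gives max(100, k + 30).
- k = 0: 90 against 100, so 8.10.1 ends 10 days earlier.
- k = 10: both give 100.
- k = 28: 118 against 100, so 8.10.1 ends 18 days later.
- k = 70: 160 against 100, so 8.10.1 ends 60 days later, and the difference stays at 60 for larger k.

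Within the 100-day IMAE window the disputed stretch is max(0, 10 − k), at most 10 days, and it concerns only serious IMAEs judged unrelated.

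**DLTs.** The DLT window is 42 days. A participant counted as free of DLT has had two nivolumab doses, which the synopsis requires to be at least 19 days apart. The second is on day 20 at the earliest, so all-AE recording runs to at least day 20 + 30 = day 50, past day 42.

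**Weight of one event.** Seven were enrolled. If all seven are in the Safety Analysis Set, one participant is 1/7 = 14.3 percentage points in a total-column row; with six it would be 1/6 = 16.7. A missed event moves a row only if it is that participant's sole qualifying event there.

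**The case against.** The strongest reply is that safety follow-up does reach day 100. The synopsis and protocol 4.1.1.5 say participants are followed for a further 100 (+5) days after immunotherapy, and SAP 1.2.1 describes the 100-day visit with no stop at new therapy. Protocol 8.7 has every AE assessed for immune mediation and sets no time limit, and 8.10.1 also lists events at any time after first administration. Sites may well have entered late non-serious events. That possibility stands, and it is why the point is possible under-counting. It does not remove the mismatch. None of these passages requires non-serious events to be recorded after the 30-day period, and an unlimited reading of the bullet in 8.10.1 would make the 30- and 90-day limits beside it pointless.

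It is also fair to say that the SAP definition follows protocol 10.1.6.2 and only adds events: any late IMAE that was recorded is counted. A reader might infer that the 100-day window is itself wrong. It is not; the fault lies in pairing it with a shorter recording rule.

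Practical weight is limited too. Seven participants were enrolled, the study has ended early, there are no hypotheses, and TEAEs are listed individually with onset dates. The 70-day figure is the extreme case of all drugs stopping together. All of this stands and keeps the point modest.

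**Conclusion.** The mismatch is real and worth fixing. The 100-day IMAE window is not matched by required recording of non-serious events for max(0, 70 − k) days: at most 70, or 65 on the 35-day reading, and none once ivosidenib has outlasted nivolumab by 70 days. The TEAE tables may under-count late non-serious IMAEs, and capture may be uneven between participants.

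The result rests on the written rules. The protocol's figure of AE reporting rules (Figure (8.10.1) 1) is not available in the public text.

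Three stronger readings are tempting and not supported:
- **Events were lost, or toxicity is understated by a known amount.** The documents set minimum recording requirements and do not show what sites entered, so the number missed cannot be derived.
- **No planned output discloses the limit.** SAP section 1 puts the table and listing templates in a separate document, so this cannot be established.
- **UK sites recorded AEs at the 100-day visit and other sites did not.** This would rest on where a mark falls in the Adverse Events row of two schedules whose column layout is not reliable in the available text. Footnote 24 sets the same rule in both.

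The SAE conflict is real but small inside the IMAE window.

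**What to change.** **Participants still in follow-up.** Align footnote 24 (both copies) and 8.10.1 so that every IMAE, serious or not, is recorded through 100 days after last immunotherapy, using the existing 100-day visit. The gap is then 0 for every k. State in the protocol and SAP whether recording and the IMAE window both end at new anti-cancer therapy.

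**Participants already past that point.** Add a footnote to the TEAE tables: beyond 30 days after the last dose of any study drug, the protocol required recording of SAEs only, and SAEs not judged related only until new anti-cancer therapy, so non-serious IMAEs in this period may be incomplete. In the TEAE listing, flag IMAEs with onset more than 30 days after the last dose of any study drug.

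**Secondary.** Reconcile the two SAE limits, including the dose from which each is counted.

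**Cost.** Wording changes in two protocol places, one table footnote, and one flag derived from onset dates already planned for the listing. For anyone still followed there is minor extra AE entry, and reported toxicity may rise slightly. The termination letter is dated 21 August 2024, so for many or all participants only the footnote and flag may still be possible.

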5.4.2. Death

A listing for deaths, along with the cause of death, will be provided for the following categories:

- On-treatment death: Deaths after the first dose of any IMP and on or before 30 days after the last dose of IMPs.
- Post-treatment death: Deaths more than 30 days after the last dose of IMPs.

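### The 30-day limit on on-treatment death can leave a fatal immune-mediated TEAE out of the fatal-TEAE row and listing, although such events count as on-treatment to 100 days after nivolumab

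*SAP*

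**What the plan says.** **Window for immune-mediated events.** SAP 4.2 gives a general on-treatment period of 30 days after the last dose, but for immune-mediated adverse events (IMAEs) it is "the time from the date of the first dose of any IMP to 100 days from the last dose of nivolumab". SAP 5.4.1.2 carries this into the TEAE definition, which runs to "the last nivolumab administration + 100 days (included) for IMAEs". Protocol 10.1.6.2 has the same two-part rule.

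**Window for deaths.** SAP 5.4.2 has a single cut for all causes: "On-treatment death: Deaths after the first dose of any IMP and on or before 30 days after the last dose of IMPs", and then "Post-treatment death: Deaths more than 30 days after the last dose of IMPs". It makes no exception for immune-mediated events. I read the last dose of IMPs as the last dose of whichever of the three drugs stopped last.

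**Where the death window is used.** The fatal category in the overall adverse event summary (SAP 5.4.1.2) is "TEAEs leading to on-treatment deaths". The listings are set out as follows: "Listings will be provided for TEAEs, SAEs, TEAEs leading to treatment discontinuation of any study drug, and TEAEs leading to on-treatment death". No other row or TEAE listing is defined by fatal outcome.

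**Protocol counterpart.** Protocol 10.1.6.2.1 also plans a summary of adverse events leading to on-treatment death. It gives no separate 30-day definition of such a death, so the only on-treatment definition to apply is the one in 10.1.6.2, with its 100-day extension for IMAEs. SAP section 7 declares no change from the protocol.

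**The concern.** On-treatment has two meanings in the same SAP. An immune-mediated event can be treatment-emergent and on-treatment under 4.2 and 5.4.1.2, while the death it causes is post-treatment under 5.4.2. Such an event is then missing from the one summary row and the one TEAE listing meant to isolate fatal events.

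The case is foreseeable. Protocol 8.7 says that immune-related events may appear several months after the last nivolumab or ipilimumab dose.

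Adverse events and SAEs are primary endpoints of the Safety Lead-in phase. SAP section 5 drops most tables and figures but keeps the adverse event summaries. A reader who finds zero in the fatal row and a Grade 5 TEAE in the table by system organ class, preferred term and severity could not tell whether this is an error or the result of a definition.

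**Working it through.** The plan states no figure on this point, so there is nothing to reproduce. The check compares the windows by day count.

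**Inputs**
- Day 0 is the date of last nivolumab.
- An IMAE is a TEAE up to Day 100 (SAP 4.2 and 5.4.1.2).
- A death is on-treatment up to 30 days after the last dose of any study drug (SAP 5.4.2).
- L is the number of days from last nivolumab to the last dose of any study drug. Protocol 8.12.2 does not allow ipilimumab to continue once nivolumab is discontinued, but ivosidenib may continue, so L depends on ivosidenib.

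**Formula**
- Last day on which a death is on-treatment: L + 30.
- Days inside the IMAE window on which a death is not on-treatment: max(0, 100 − (L + 30)) = max(0, 70 − L).

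**Results** (the values of L are illustrative; the documents give no actual dosing dates)

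| L (days) | Days of death left out | Gap (days) |
|---|---|---|
| 0 | 31 to 100 | 70 |
| 20 | 51 to 100 | 50 |
| 27 | 58 to 100 | 43 |
| 60 | 91 to 100 | 10 |
| 69 | 100 | 1 |
| 70 or more | none | 0 |

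L = 20 is ivosidenib taken to the end of a 21-day cycle with nivolumab on Day 1 (21 − 1). L = 27 is the same for a 28-day cycle (28 − 1).

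**Example.** All drugs stop on the same day (L = 0). Immune-mediated hepatitis starts on Day 20 and the participant dies of it on Day 40. Day 40 is within 100, so this is a Grade 5 TEAE. Day 40 is after Day 30, so the death is post-treatment. The event is in the severity table but not in the fatal row or its listing.

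**Effect of one such death.** SAP section 5 reports 7 participants enrolled. If all 7 are in the Safety Analysis Set, the row moves from 0/7 (0%) to 1/7 = 14.3%.

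**Effect of aligning the windows.** If deaths from IMAEs counted as on-treatment to Day 100, the gap inside the IMAE window would be 0 for every L. A death after Day 100 from an IMAE that began inside the window would still be left out.

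**The case against.** The strongest reply is that nothing is concealed. SAP 5.4.2 lists post-treatment as well as on-treatment deaths, each with its cause. A late fatal IMAE also appears in the TEAE and SAE listings with onset and outcome, in the Grade 3 or higher and SAE rows, and in the severity table. With 7 participants and a report built mainly on listings, every death can be seen individually. All of this stands. A reader might infer that the death vanishes from the report; the SAP does not support that. Only one summary row and its matching listing are affected.

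A reader might also infer that every fatal IMAE with onset 31 to 100 days after nivolumab is left out. That is too broad, because the 30 days run from the last dose of any drug. Protocol 4.1.1.3 and 8.12.2 let ivosidenib continue after nivolumab stops, and at L of 70 or more there is no gap within the 100 days.

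The row is labelled by on-treatment death, as the protocol planned, so a zero would be true to its label. That is fair as far as the label goes. It does not remove the conflict, because SAP 4.2 and protocol 10.1.6.2 give on-treatment a longer meaning for exactly these events.

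For non-immune events the problem is less certain. A TEAE that starts within 30 days and is fatal later would miss the row. But protocol 8.10.2.2 asks for a new form when severity worsens, while 8.8 updates severity on a persistent event. Under the first rule, the Grade 5 record could itself fall outside the 30-day TEAE window. The point therefore rests on immune-mediated events.

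Finally, no remaining decision depends on this row. Enrollment has stopped, there is no Expansion phase, and the DLT window is 42 days. This limits the severity.

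**Conclusion.** The inconsistency is real and minor. SAP 5.4.2 conflicts with SAP 4.2, SAP 5.4.1.2 and protocol 10.1.6.2 on how long an immune-mediated event remains on-treatment. As a result, the fatal-TEAE row and listing can omit a fatal immune-mediated TEAE that other outputs of the same report show.

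The gap is max(0, 70 − L) days, at most 70. The 14.3% assumes that all 7 enrolled participants were treated and are in the Safety Analysis Set; the documents give the number enrolled, not the size of that set. It is a what-if: no document shows that such a death occurred.

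Nor do the documents support ranking fatal immune toxicity as the main risk of this combination. Protocol 2.5 gives Grade 3 or 4 immune-related events in 15% (6 of 39) in the earlier nivolumab plus ipilimumab study, and no figure for fatal immune toxicity. The point does not need that ranking.

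**What to change.** Either of two changes would do.

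1. Reconcile SAP 5.4.2 with 4.2 and 5.4.1.2, so that a death from an IMAE counts as on-treatment to 100 days after last nivolumab. This is the smaller change and follows the protocol, but it leaves out deaths after Day 100 from events that began in the window.
2. More simply, define the summary row and the listing as TEAEs with fatal outcome (Grade 5), whatever the date of death. This goes a little further than the conflict requires, but it makes the row agree with the severity table.

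In both cases, keep the on-treatment and post-treatment split in the death listing and add a flag for deaths due to a TEAE.

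The cost is SAP and table-shell wording. Severity, outcome and cause of death are already planned outputs, so no new data are needed. The fatal count can only stay the same or rise.
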